## 14.4.5 Usability Sample Size

Descriptive usability analyses benefit from larger samples.

- Able to detect differences in usability scores (effect size d~0.5) with 80% power.
- **n = 100–125** provides a 90% usability rating with:
  - ±6% precision around usability proportions (95% CI).
  - Adequate numbers for subgroup comparisons.

## 14.5 Determination of Acceptable Usability

The Likert scale used to indicate usability is a 5-point scale where 3 represents a neutral or standard assessment. The scale allows subjects and clinicians to select a better or worse assessment.

The overall usability score will be computed as the mean of eight individual 5-point Likert items related to setup, ease of use, interpretation and satisfaction. This continuous usability index (range 1-5) will be summarized using mean and standard deviation. The null hypothesis is that the test usability index is no different from the population index of 3. Usability will be considered acceptable if the mean score is significantly greater than 3, assessed using a one-sample t-test. Internal consistency of the scale will be evaluated using Cronbach's alpha.

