## 11.1 Figure 1: Overview of Study Visit Process

The CI/RN or designee will observe the subject using purpleDx and will use a simple tick-box Likert scale to answer a series of five questions about their ability to use the device. Each subject will also be asked to answer the same five questions using the simple tick-box scale to rate their ease of using the app (see Appendix 8 Section A – Device Setup and Use).

The CI/RN or designee will answer 3 additional questions (see Appendix 8 Section B – Time and Workflow).

Lastly, the CI/RN or designee and each subject will be asked to complete two open feedback questions to provide details of any difficulties or issues encountered during the process for setup, performing the scan, obtaining and recording results (see Appendix 8 Section C – Open Feedback).

All responses and required study information will be recorded in each subject's medical records or agreed form of source documentation. Data from purpleDx will be automatically uploaded to the Sponsor's database in the cloud. This information will only be identifiable by the subject study number i.e. no Patient Identifiable Data (PID) will be included.

Upon completion of the subject's visit, the CI/RN or designee will transcribe the information from any source documentation into the electronic Case Record Form (eCRF) within pre-agreed timelines (e.g. within 1 week of the date of the study timepoint).

The source documentation will be made available for external monitoring to ensure accuracy and validity of data transcribed into the eCRF.

All source documentation and the ISF must be kept for at least 10 years after the device is last placed on the market to comply with the medical device marketing requirements of regulators following completion of the study. Archival processes will be agreed between CUH and the Sponsor as part of the negotiation process to establish the Clinical Trial Agreement and ensure access can be arranged if required in future for auditing purposes.

The Sponsor will provide a secure database to act as the eCRF for the study raw data. Access to the eCRF will be password protected, and no patient identifiable data will be held within the eCRF. Each subject will only be identifiable by subject study number.

To access the eCRF, each user will require access rights to be granted by the Sponsor.

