## 20.8.2 Section B – Time and Workflow (for Clinician only)

These questions should be answered by the clinician (CI/RN/designee) by ticking or circling the appropriate point on a scale of 1 to 5 as shown below:

6) How much time did it take to get a successful reading using purpleDx (approximate seconds)?

seconds

7) How would you rate the purpleDx device's impact on workflow in a busy Emergency Department setting?

8) Did the purpleDx device require technical assistance to use?

Yes No If Yes, please explain:

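### The usability index is defined as the mean of eight 5-point items, but patients answer five and clinicians at most six, so it cannot be computed as written

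*Protocol*

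**What the plan says.** Section 14.5 builds the usability score as the "mean of eight individual 5-point Likert items related to setup, ease of use, interpretation and satisfaction". It continues: "This continuous usability index (range 1-5) will be summarized using mean and standard deviation". The success rule is: "Usability will be considered acceptable if the mean score is significantly greater than 3, assessed using a one-sample t-test". Internal consistency is to be checked with Cronbach's alpha. The same section makes clear that both groups use the scale: "The scale allows subjects and clinicians to select a better or worse assessment".

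Section 11.1 describes how the ratings are collected. The investigator, research nurse or designee "will use a simple tick-box Likert scale to answer a series of five questions about their ability to use the device". For patients: "Each subject will also be asked to answer the same five questions using the simple tick-box scale". The clinician then answers three further questions, and both groups complete two open ones.

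Appendix 8 prints the questionnaire. Section A (questions 1 to 5) goes to both groups on a 1 to 5 scale. Section B (questions 6 to 8) is for the clinician only. Its lead-in says that the answers are given on a 1 to 5 scale, yet question 6 asks "How much time did it take to get a successful reading using purpleDx (approximate seconds" and question 8 asks "Did the purpleDx device require technical assistance to use", with Yes/No boxes. Section C is free text.

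**The concern.** Section 14.5 is the only place where usability has a pass or fail rule. Ease of use is among the primary objectives in Section 9.1, and usability to subjects and staff is a secondary endpoint in Section 10.2. The study is meant to support a marketing application.

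If the defined index does not match the questionnaire, the analyst must decide which items to average and whether patients and clinicians are pooled or kept apart. Section 14.4.1 provides for a review of preliminary data once 150 patients are recruited, so those choices could be made after data have been seen. Cronbach's alpha also depends on which items make up the scale, so it is undefined until the item set is fixed.

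**Working it through.** The check is a count of questionnaire items by respondent and response format. The inputs are Section 11.1 and Appendix 8 (20.8.1 to 20.8.3).

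| Question | Answered by | Response format | 5-point item? |
|---|---|---|---|
| 1 to 5 (Section A) | Patient and clinician | Scale of 1 to 5 | Yes, five items |
| 6 (Section B) | Clinician | Time in seconds | No |
| 7 (Section B) | Clinician | Rating of workflow impact | Probably (see below) |
| 8 (Section B) | Clinician | Yes/No with explanation | No |
| 9 and 10 (Section C) | Patient and clinician | Free text | No |

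**Trying to reproduce the plan's eight:**

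- Patient 5-point items: 5.
- Clinician 5-point items: 5 + 1 = 6 if question 7 is on the 1 to 5 scale, and 5 if it is not.
- Patient and clinician Section A sheets taken together: 5 + 5 = 10, or 11 with question 7.
- All numbered questions in Sections A and B, whatever their format: 5 + 3 = 8.

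Only the last count gives eight. It is probably where the figure came from, though that is an inference. It does not meet the definition in Section 14.5, because two of the eight are not 5-point items and patients answer only five of them.

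**Status of question 7.** The response-scale figures are missing from the text at hand, and no options are visible for this question. It counts as a 5-point item only on the strength of the Section B lead-in, which is visibly wrong for questions 6 and 8. Six is therefore an upper limit for clinicians. If question 7 has another format, the clinician count is five and the mismatch is larger.

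**Missing figures do not explain the gap.** The formats of questions 6 and 8 survive as text, and neither is a 5-point scale.

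**One score, two groups.** Section 14.5 names a single overall score and says that both groups use the scale. Section 11.1 and Appendix 8 give the groups different question sets. Nothing says whether the score is computed per patient, per clinician form or per pair, and this determines the number of observations in the t-test.

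**The case against.** The strongest defence is that the damage is small. The five Section A items are defined, scaled 1 to 5 and collected from every respondent who completes the form. Their mean lies in the stated range and can be tested against 3. Only the word eight and the silence on pooling need repair. Sections 14.3.4 and 14.4.5 also treat usability largely as descriptive. All of this stands, and it limits the weight of the point. It does not remove it, because a mean of five items is not the index that Section 14.5 defines.

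A separate statistical analysis plan might settle the matter. Section 14.5, however, already fixes the item count, range, test and success rule. The fault is a wrong statement, not an omitted detail.

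Two stronger readings are tempting, and the protocol does not support either.

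- A reader might infer that the time in seconds would be averaged in and swamp the score. With every rating at the neutral 3, question 6 at 60 seconds and question 8 coded 1 (all assumed), the mean would be (18 + 60 + 1)/8 = 9.9, which would clear the threshold of 3 automatically. Section 14.5 excludes this analysis by limiting the index to 5-point items with a range of 1 to 5, and Section 14.3.4 lists setup time as a separate summary. The figure shows only that questions 1 to 8 cannot be the intended set.
- A reader might infer a specific understatement of the clinician standard error, because the same staff rate many patients. The protocol gives neither the number of raters nor any within-rater correlation, so any multiplier would rest wholly on assumed values. Section 14.5 also does not say that clinician scores are tested on their own. What remains is the qualitative point that repeated ratings by the same single-site staff should not be treated as independent.

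**Conclusion.** The contradiction is real and follows from counting alone. Section 14.5 requires eight 5-point items; patients have five and clinicians five or at most six. The index cannot be computed as defined, and its unit of analysis is not settled. The count for patients needs no assumption. The upper figure for clinicians assumes that question 7 uses the 1 to 5 scale.

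No data are lost, and a usable index can be formed from what is already collected. The agreement analyses, including the primary one for peak expiratory flow, are unaffected. This should be fixed, preferably before any data are reviewed, but it does not threaten the study's main conclusion.

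**What to change.** In Section 14.5:

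1. Replace the eight-item definition with a patient index equal to the mean of items 1 to 5, one value per subject, tested against 3 with the one-sample t-test already planned.
2. Define a separate clinician index as the mean of items 1 to 5, adding question 7 only if it is confirmed as a 1 to 5 item. Report it descriptively, because the same staff are likely to rate many subjects. A cluster-robust standard error would be unreliable if there are only a few raters.
3. Summarise question 6 as a time, for example the median, and question 8 as a proportion.
4. Compute Cronbach's alpha separately for the patient scale and the clinician scale.

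In Appendix 8, correct the Section B lead-in so that it no longer describes all three questions as 1 to 5 ratings.

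The cost is protocol wording only. There are no new data, no change to the visit and no change to the sample size. The wording should be settled before the preliminary data review described in Section 14.4.1.

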- Confirmation of no known pregnancy in women of child-bearing potential (WOCBP); see Appendix 5
- Light Level (measured using device provided by Sponsor)
- Sitting or Reclining (and angle of recline if reclining)
- Peak expiratory flow (PEF) measured by purpleDx
- Peak expiratory flow (PEF) measured by conventional equipment (provided by Sponsor)
- Forced expiratory flow in one second (FEV1) measured by purpleDx
- Forced expiratory flow in one second (FEV1) measured by conventional equipment
- Respiratory rate (RR) measured by purpleDx
- Respiratory rate (RR) measured by manual count / visual inspection
- Heart rate (HR) measured by purpleDx
- Heart rate (HR) measured by conventional equipment
- Nurse/clinician assessment of subjects' ability to use purpleDx
- Subject evaluation of ease of using purpleDx
- Difficulties using purpleDx
- Adverse Event information
- Confirmation of new disposable mouthpiece for each subject's spirometry assessments.

During each purpleDx measurement, the following will also be recorded by the CI/RN or designee:

- Participant behaviour during recording, such as movement, talking, coughing,
- Facial obstructions, such as glasses, hats, beards, makeup, etc
- Chest obstructions, such as lanyards, loose clothing, top pattern (uniform versus patterned), etc
- Specific technical difficulties that may be encountered

[figure not shown]

Details of any difficulties in following instructions.

The CI/RN or designee will use the light meter (see details in Appendix 6) provided by the Sponsor to ensure lighting levels are in the required range to allow purpleDx to function and will demonstrate how to use the purpleDx app to the subject. The Sponsor will provide the site with an iPhone containing the purpleDx app already downloaded and ready for use.

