## 20.8.1 Section A – Device Setup and Use (for Patients and Clinician)

These questions should be answered by the subject and the clinician (CI/RN/designee) on separate sheets of paper, by ticking or circling the appropriate point on a scale of 1 to 5 as shown below:

[figure not shown]
1) How easy was it to understand the instructions for using the purpleDx device?

[figure not shown]
2) How easy was it to perform the test with purpleDx (such as sit still / follow prompts)?

3) How confident are you in the accuracy of the purpleDx device reading?

[figure not shown]

4) How comfortable was the device to use?

5) Would you be willing to use this purpleDx device again at a future visit?

[figure not shown]

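### The section 14.5 usability t-test does not separate subject from clinician sheets; to the extent that clinician sheets enter it, repeat ratings by the same staff count as independent

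*Protocol*

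**What the plan says.** Section 14.5 (Determination of Acceptable Usability) defines the index: "The overall usability score will be computed as the mean of eight individual 5-point Likert items". It names both groups as users of the scale: "The scale allows subjects and clinicians to select a better or worse assessment". The decision rule follows: "Usability will be considered acceptable if the mean score is significantly greater than 3, assessed using a one-sample t-test". The section does not say whose sheets are analysed and has no term for the rater.

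Section 11.1 describes how the data arise. A staff member watches each subject and completes a tick-box sheet, and the stated task is this: "answer a series of five questions about their ability to use the device". Each subject completes those five items as well. Then, for staff only: "The CI/RN or designee will answer 3 additional questions". The questions are in Appendix 8: Section A (items 1 to 5) for both groups, Section B (items 6 to 8) for the clinician alone.

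Section 11.0 lists the data collected for each subject, including "Nurse/clinician assessment of subjects' ability to use purpleDx". No code for the person who gave that rating is listed. The study has one site (section 11.0) and aims for 150 analysable data sets from at most 160 subjects (section 14.4.1).

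**The concern.** A one-sample t-test needs independent scores. Subject sheets meet this, with one person and one sheet each. Clinician sheets do not if the same staff member fills in many of them. Each rater has a personal level of approval of the device, and this recurs on every sheet that rater completes. The test would then count sheets when the information depends largely on the number of people.

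The wording of some items strengthens the link. On the staff sheet, item 3 asks about the respondent's confidence in the accuracy of the reading, item 5 asks "Would you be willing to use this purpleDx device again at a future visit", and item 7 asks for a view of the effect on department workflow. These invite the rater's own opinion, whereas sections 11.0 and 11.1 describe a rating of the subject's ability. A rater effect would cause clustering under either reading.

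At stake is the conclusion that usability is acceptable. Section 9.1 places ease of use, as judged by subjects and clinical staff, among the primary objectives. Section 10.2 makes usability a secondary endpoint. The PEF conclusion is not affected.

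**Working it through.** **1. The plan's own usability figures.** Section 14.4.5 states ±6% precision around a 90% rating with n = 100–125, and 80% power for d of about 0.5.

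- Precision: 1.96 × √(0.9 × 0.1 / n) gives 5.9% at n = 100 and 5.3% at n = 125. This reproduces.
- Power: a two-group comparison at d = 0.5 needs 63 per group (126 in total), with 79.8% power at 125 in total. This reproduces as a two-group figure.
- The one-sample t-test that section 14.5 names needs only about 34 independent ratings for 80% power at d = 0.5, and has over 99% power at 100.

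All of these assume independent ratings.

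**2. Which sheet can supply eight items.** Subjects answer 5 closed questions; staff answer 5 + 3 = 8. A count of eight therefore fits only the clinician sheet. Item 6 is a time in seconds and item 8 is Yes/No, so that sheet offers at most 8 − 2 = 6 items on a 5-point scale. The index as written cannot be formed from either sheet, but its item count points to the clinician one.

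**3. Effect of repeat raters.** Inputs: N = 150 sheets (section 14.4.1). Assumed, because the protocol does not give them: K raters with equal workloads, and a within-rater correlation (ICC). Sheets per rater m = 150/K; design effect DE = 1 + (m − 1) × ICC; effective number of ratings = 150/DE.

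- Worst corner, K = 3 and ICC 0.5: m = 50, DE = 1 + 49 × 0.5 = 25.5, effective n = 150/25.5 = 5.9.
- Mildest corner, K = 10 and ICC 0.05: m = 15, DE = 1 + 14 × 0.05 = 1.70, effective n = 150/1.70 = 88.2.

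The false-positive rates come from simulation (20,000 runs per setting). The true mean was set at exactly 3, with a random rater effect, and the naive t-test was applied to all 150 sheets. The nominal upper-tail rate is 2.5%.

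| Raters | ICC | Effective n | Upper-tail false positives |
|---|---|---|---|
| 3 | 0.05 | 43.5 | 15% |
| 3 | 0.1 | 25.4 | 21% |
| 3 | 0.3 | 9.6 | 33% |
| 3 | 0.5 | 5.9 | 37% |
| 5 | 0.05 | 61.2 | 10% |
| 5 | 0.1 | 38.5 | 17% |
| 5 | 0.3 | 15.5 | 28% |
| 5 | 0.5 | 9.7 | 32% |
| 10 | 0.05 | 88.2 | 7% |
| 10 | 0.1 | 62.5 | 10% |
| 10 | 0.3 | 28.8 | 19% |
| 10 | 0.5 | 18.8 | 25% |

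With ICC = 0 the simulated rate was 2.5% to 2.6%, as it should be.

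**4. Outside the range.** With 20 raters and ICC 0.05, m = 7.5 and DE = 1 + 6.5 × 0.05 = 1.33. The normal approximation gives an upper-tail rate of about 4.4%. The problem shrinks as raters increase or the ICC falls.

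**The case against.** The strongest reply is that section 14.5 never says clinician sheets are tested or pooled, and the protocol sets no separate acceptability decision for clinicians. If the test used subject sheets only, there would be no clustering. That stands, and it is why the point is conditional. It does not clear the plan, because the section names both groups, separates neither, and uses an item count that only the clinician sheet can approach.

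A reader might infer that a handful of staff rate everyone. The documents do not support this as fact. No section gives the number of raters, and the designee role is open-ended. One site makes repeat raters likely without fixing how many.

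A reader might also infer that the clustering could never be corrected. This is not shown. The text of Appendix 8 describes no rater field, but the scale graphics were not available here, so a printed field cannot be excluded. Staff answer on separate sheets, responses are kept as source documents (section 11.1), and Appendix 10 requires a delegation log and signature sheet. Section 16.5.1 limits recording to the data points outlined, but that rule concerns patient data and does not clearly bar a staff code. What can be said is that the dataset as specified cannot adjust for rater.

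Nor does every item on the staff sheet record a fixed opinion. Item 2 concerns performance of the test, item 1 can be read that way by an observer, and items 6 and 8 belong to the encounter. Finally, sections 14.3.4 and 14.4.5 treat usability as largely descriptive. Section 14.5 nevertheless attaches a significance test and a pass rule to it, under a chapter that the protocol itself titles as its statistical analysis plan.

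**Conclusion.** The point holds in conditional form. Section 14.5 fixes a decision rule without saying whose ratings enter it. Any clinician sheets that do enter are treated as independent although staff may contribute many each, so the standard error is too small. Under 3 to 10 raters, equal workloads and ICC 0.05 to 0.5, 150 sheets are worth about 6 to 88 independent ratings, and a true mean of 3 would be declared acceptable about 7% to 37% of the time instead of 2.5%. These figures rest wholly on the assumed rater count and ICC, and apply at a true mean of exactly 3. The direction of the error does not depend on them unless the ICC is essentially zero. Subject-completed ratings are unaffected. The change should be made before recruitment: it concerns a stated pass rule, but one outside the PEF endpoint.

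**What to change.** 1. Record an anonymous staff code on each clinician sheet and add it to the data items in section 11.0.
2. Base the section 14.5 t-test on the subject-completed sheets, and redefine the index as the mean of the five Section A items that subjects answer. With about 150 subjects and roughly 34 needed for 80% power at d = 0.5, power is ample.
3. Report clinician ratings separately, still as part of the usability endpoint, either summarised per rater or analysed with rater as the cluster. With very few raters a formal test has little basis.
4. Reconcile sections 11.0 and 11.1, where staff rate the subject's ability, with Appendix 8, where items 3, 5 and 7 ask for the rater's own view.

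The cost is one field on the form, a short change to section 14.5 and small wording edits. The downside is that the clinician result becomes descriptive or has wider intervals.

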## 14.6 Sensitivity Testing

#### Within % criteria

It is intended with the data that we will refine the 'within x% criteria' by computing the proportion of paired readings within a range of limits e.g.  $\pm$  5%,  $\pm$  10%,  $\pm$  20%. By plotting these as a cumulative agreement graph, this will show how the devices converge as the tolerance band widens and enable users to decide how best to implement the device for their patients/subjects.

For each tolerance (e.g. 5%, 10%, 20%), we will also compute the **Wilson 95% CI** for the proportion within limit.

#### The Bland Altman plot

This is the industry standard for quantifying agreement. This allows systematic bias and spread to be visualised.

## 14.7 Handling of Missing Data

#### 14.7.1 General Approach

• Every effort will be made to minimize missing data by thorough training of staff, checking of data at the point of entry, and rapid feedback to clinical teams.

- Missing data are anticipated to arise primarily from:
  - Patient inability to perform the measurement correctly,
  - Equipment malfunction or technical failure,
  - Clinician time pressure preventing data recording.

